8.6 Follow-up of subjects withdrawn from treatment

All patient files will be examined 12 months and ~5 years after inclusion (§8.8, p58)

8.7 Premature termination of the study (interim-analysis)

The false-negative FDG-PET/CT ratio is expected to be around 1.3%, but we accept a falsenegative ratio of up to 5% (i.e. the a priori risk of malignancy in any thyroid nodule). After inclusion and surgery of 22 (50%) patients in the control study-arm, an interim analysis will be performed by the safety committee (§9.5: Data Safety Monitoring Board (DSMB) / Safety Committee, p62). In case 4 or more of these first 22 patients (π_1 *=18.2%) in the control studyarm have a false-negative FDG-PET/CT, the study will be terminated preliminarily and the physicians of all PET-negative patients in the experimental study arm will be informed to advise them to undergo diagnostic (hemi)thyroidectomy. This number is based on the cumulative binomial distribution, by solving:

$$\sum_{n=X}^{n=N} \binom{N}{X} \cdot p^X \cdot (1-p)^{N-X} \leq \alpha$$

With N=22, p=0.05 and α =0.025 (Bonferroni-adjusted), resulting in X≥4. Single-sided testing was used. Figure 7, p57.

8.8 Mid- to long-term follow-up

The duration of short-term follow-up since FDG-PET/CT for this study is set at 12 months, as it is expected that most treatment procedures have taken place within this period and most complications have been resolved. Primary and secondary outcome measures are therefore collected during this one-year period.

In the ideal case that no false-negative FDG-PET/CT-scans occur, it is safe to assume that recurrences and other mid- to long-term sequelae would occur in same fractions in both study arms. However, a one-year follow-up period could be considered too short to conclude a false-negative-fraction for FDG-PET/CT as a delayed diagnosis of malignancy might be made over a year after initial FNAC as DTC usually follows an indolent growth. Also, the costs and utilities (health related quality of life) attributed to delayed treatment would not be completely incorporated in the study most likely leading to an underestimation of false-negative rates, an underestimation of costs, and an overestimation of utility in de experimental study arm due to censoring.

Therefore, five year after the inclusion of the last patient a retrospective study will be conducted using patient files completed with contact with the general practitioners of these patients to investigate the mid- to long-term effects of our intervention.

All treating physicians are aware that about 3.6% of all negative FDG-PET/CT scans are falsenegative (1.3% of all patients included in the study). The short-term follow-up will distinguish a portion of these patients with thyroid malignancy, but probably not all. Therefore, the treating physicians are advised to follow-up the nodules for at least 5 years like "benign nodules" in the ATA-guidelines [6], recommendation 14:

- (a) It is recommended that all benign thyroid nodules be followed with serial US examinations 6–18 months after the initial FNAB. If nodule size is stable (i.e., no more than a 50% change in volume or <20% increase in at least two nodule dimensions in solid nodules or in the solid portion of mixed cystic–solid nodules), the interval before the next follow-up clinical examination or US may be longer, e.g., every 3–5 years.
- (b) If there is evidence for nodule growth either by palpation or sonographically (more than a 50% change in volume or a 20% increase in at least two nodule dimensions with a minimal increase of 2mm in solid nodules or in the solid portion of mixed cystic–solid nodules), the FNA should be repeated, preferably with US guidance.

The malignancy rate after a reassuring confirmatory US in these patients is less than 3.6%, which is similar to Bethesda cat. II (benign, malignancy risk 0-3%) or Bethesda cat. I (nondiagnostic or unsatisfactory, malignancy risk 1-4%).

Unlike with the US and FNA during the inclusion phase, with the (first) confirmatory US 12 months after a negative FDG-PET/CT (in the experimental study arm) the treating physician is free in using additional diagnostic tests such as a gene-expression classifier, mutational marker panel, US elastography, etc. Apart from this confirmatory US, all other investigations are outside the scope of this project.

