3. STUDY DESIGN

A partially-blinded, prospective, multi-centre, block-randomised controlled trial (RCT) is designed. After obtaining written informed consent, patients are registered centrally, FNAC is reviewed centrally and thereafter patients are randomised to either the experimental study-arm (arm A: FDG-PET/CT driven management decisions) or a control study-arm (arm B: surgery regardless FDG-PET/CT result) using a 2:1 allocation ratio. The latter is performed both for methodological purposes (the treatment of the subjects in the control study arm is well investigated and described before) and to satisfy the assumption that patient prefer the experimental study-arm. The result of randomization is blinded to the treating physicians and central FDG-PET/CT review committee. Allocation is adaptively stratified using the minimisation method on the centre of inclusion and the most prognostic features of DTC known at this stage of patient work-up: (US) lesion size (0-10 mm/11-20 mm/21-40 mm/40+ mm), patient sex, patient age (<45yr, \geq 45yr) and Bethesda classification according to central review committee (atypia of unknown significance/follicular lesion of unknown significance (III) or (suspicion) for a follicular neoplasia (IV)).

Based on the study arm allocation and PET result, treating physicians will either be told to cancel scheduled diagnostic thyroid surgery (allocation to the experimental arm with a negative FDG-PET/CT at central review or ~32/132 patients) or to proceed with surgery (all other cases or 100/132 patients). In case surgery is cancelled the patients need to be followed-up by watchful waiting and a confirmatory ultrasonography (including FNAC) after 12 months. Patient allocation will not be disclosed to prevent study withdrawal, however in case surgery is cancelled unblinding is unavoidable (~25% of all included patients).

The Gold Standard is histology, revised by a (central) dedicated pathologist panel, obtained from surgery or 12-months follow-up, including US (+FNAC). All patients will be followed for at least 12 months after FDG-PET/CT to ensure all direct costs and complications are noted. Five years after inclusion of the last patient, long-term follow-up will be determined based on patient file review and contact with the general practitioner (flowchart Figure 1, p34 and

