8. METHODS

8.1 Study parameters/endpoints

8.1.1 Main study parameter/endpoint

The fraction of unbeneficial treatment (i.e. surgery in benign disease plus watchful waiting in malignant disease) in both study arms based on intention-to-treat.

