8.3.2 Confirmatory Neck US

A confirmatory US of the neck is performed locally by a dedicated head and neck radiologist in all FDG-PET-negative patients in the experimental arm, 12 months after inclusion. No preparations are needed. An ultrasound is performed in supine position after application of conducting gel. If nodule size is stable (i.e., no more than a 50% change in volume or <20% increase in at least two nodule dimensions in solid nodules or in the solid portion of mixed cystic-solid nodules), the interval before the next follow-up clinical examination or US may be longer, e.g., every 3–5 years. If there is evidence for nodule growth either by palpation or on US (more than a 50% change in volume or a 20% increase in at least two nodule dimensions with a minimal increase of 2 mm in solid nodules or in the solid portion of mixed cystic-solid nodules), the FNAC should preferably be repeated (on discretion of the physician performing the US), preferably under US guidance: the neck will be cleaned with alcohol and a fine-needle will be inserted into the lesion, causing no more pain than a regular venapunction. Other indication for FNAC are also on discretion of the physician performing the US, but should take into account prior US results. The patient is treated further according to the guidelines [5, 6]. Afterwards the patient can go home without any further restriction. The total examination takes around 0.5 hours. The results of the confirmatory US are known by the treating physician, PI and the patient is informed (i.e. no blinding). Patients are eligible for compensation of the travelling expenses.

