8.3.4 Cytology and histopathology analysis

In the study, cytopathology and histopathology specimens are collected. After cytopathology is collected from individual patients during FNA (prior to study inclusion), cytopathology slides are reviewed at the Radboudumc by two experienced thyroid pathologists to ensure appropriate inclusion in the study. If the first and second pathologist disagree, a third dedicated pathologist will be consulted. Consensus upon classification as either Bethesda category III or IV has to be reached before inclusion of a patient into the study (§8.2.1, p46). Cytopathology samples are returned and stored in local tissue banks at the centre where the FNA was initially performed. Before start of the study, a consensus meeting was held with the dedicated pathologists from the different centres to minimise interobserver variation.

After surgery, thyroidectomy specimens are being stored at the hospital where the surgery has been performed and will be collected at the end of the study. After surgery in all appropriate study patients is completed, histopathology specimens will be reviewed at the Radboudumc by the same experienced thyroid pathologists but an expert of the LUMC may be consulted for specific cases. Characteristics of the lesion like type of lesion, size, cell type, inflammation and vascularity will be scored (see §8.1.2, p45) in adherence to the World Health Organization guidelines [64].

Next, cytological and histopathological tissue characteristics will be analysed in relation to FDG-PET/CT findings in order to determine whether specific tissue characteristics can explain false positive or negative FDG-PET/CT results - like for instance high vascularity or cell type.

Definition of malignant and benign thyroid nodules:

A nodule is considered malignant, in case malignancy is diagnosed at the location of the nodule. All other cases are considered benign nodules.

[figure not shown]
Following advanced insights and in accordance with WHO guidelines, pre-malignant entities such as non-invasive follicular thyroid neoplasm with papillary-like nuclear features (NIFTP), follicular tumor of uncertain malignant potential (FT-UMP) and well-differentiated tumor of uncertain malignant potential (WDT-UMP) are distinguished. These are strictly considered benign though potentially precancerous lesions, for which thyroid lobectomy is justified [65, 66].

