 Table 7: Parameters describing association between variables.

Statistic:	Number		
Correlation Coefficient (R)	1	R=0?	t-test
		R=value	Fisher's z Transformation
	2	Independent	
		Dependent	
Regression Coefficients	1		t-test
	2		

 Table 8: Comparison between parameters describe association

Se, Sp, PPV and NPV will be computed using the traditional formulae, using the definition for true/false positive as described in Table 9, p67, §8.3, p48:

Sensitivity: $Se = \frac{TP}{TP+FN}$, $Specificity: Sp = \frac{TN}{TN+FP}$ Accuracy: $Acc = \frac{TP+TN}{TP+TN+FP+FN}$, $Prevalence: Prev = \frac{TP+FN}{TP+TN+FP+FN}$ Positive Predictive Value: $PPV = \frac{TP}{TP+FP}$, $Negative Predictive Value: NPV = \frac{TN}{TN+FN}$ Positive Likelihood Ratio: $LR + = \frac{Se}{1-Sp}$, $Negative Likelihood Ratio: LR - = \frac{1-Se}{Sp}$ Diagnostic Odds Ratio: $dOR = \frac{LR+}{LR-}$, $SE(LOG(dOR)) = \sqrt{\frac{1}{TP} + \frac{1}{TN} + \frac{1}{FP} + \frac{1}{FN}}$ [69]

	Disease +ve	Disease –ve
Test +ve	TP	FP
Test –ve	FN	TN

Table 9: Definition of true positive (TP), true negative (TN), false-positive (FP) and false-negative (FN).

Threshold effects of FDG-uptake in de nodules will be assessed using receiver-operating characteristic (ROC) curves and quantified using the area under the curve (AUC), as Se and Sp are inversely related. The standard error (and thus the 95%-CI) of the AUC can be computed either under a bi-negative exponential assumption (used only when the number of positive actual states is equal to the number of negative actual states) or using a non-parametric assumption (used in all other cases).

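### PET-negative experimental patients are checked mainly at month 12, as the outcome and cost window closes, so missed cancers can count as benign and flatter sensitivity and NPV

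*Protocol*

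**What the plan says.** The primary endpoint (section 8.1.1) is the fraction with unbeneficial treatment: surgery for benign disease, or watchful waiting in malignant disease. Section 8.8 sets short-term follow-up at 12 months from FDG-PET/CT and states: "Primary and secondary outcome measures are therefore collected during this one-year period". Section 10.6 uses the same 12 months for costs and QALYs.

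Controls are operated on and have histology. In the experimental arm, PET-negative patients have surgery cancelled, and section 3 makes 12-month follow-up with ultrasound and possible FNAC their reference standard. Section 8.3.2 schedules that ultrasound "in all FDG-PET-negative patients in the experimental arm, 12 months after inclusion"; section 8.8 places it differently, "with the (first) confirmatory US 12 months after a negative FDG-PET/CT". If the nodule has grown, "the FNAC should preferably be repeated (on discretion of the physician performing the US"). Section 8.3.4 calls a nodule malignant when malignancy is diagnosed at its site, and otherwise: "All other cases are considered benign nodules".

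For accuracy, section 10.3 says "Se, Sp, PPV and NPV will be computed using the traditional formulae" and does not name the arms that enter the counts. Section 8.8 acknowledges that one year may be too short, that false negatives and costs will probably be underestimated and utility overestimated in the experimental arm, and that short-term follow-up will probably not find every cancer. Its response is a retrospective file review five years after the last inclusion.

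**The concern.** A missed cancer in the experimental arm has to be suspected, sampled, operated on and read before it is firmly established. The main scheduled step that starts this sequence falls at the end of the window in which outcomes and costs are collected. Until malignancy is diagnosed, the benign default scores the patient as a true negative and the watchful waiting as beneficial. The same patient in the control arm would be scored from histology.

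The bias therefore runs one way. It lowers the unbeneficial rate and the costs in the PET-driven arm and, if that arm enters the accuracy tables, raises sensitivity and NPV. NPV is the figure on which withholding surgery rests. The protocol sees the direction of the bias, but no section feeds later findings back into the 12-month analyses.

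**Working it through.** **Inputs.** Pooled counts in Appendix IV: TP 55, TN 80, FP 87, FN 3, total 225. Planned arms (section 4.4): A = 88, B = 44. Accepted false-negative ratio (sections 8.4.1 and 8.7): 5% of patients.

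**The plan's own figures reproduce.** FN among all patients 3/225 = 1.3%; among negative scans 3/83 = 3.6%; sensitivity 55/58 = 94.8%; NPV 80/83 = 96.4%. Expected cancelled operations 88 × 83/225 = 32.5, against about 32 in section 3.

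**Model.** Let f be the true false-negative ratio and d the share of arm A missed cancers confirmed in time to count. The documents give no value for d, so it is varied from 0 to 1. Prevalence (58/225) and specificity (80/167) are held fixed.

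- Unbeneficial rate, arm A, observed = 87/225 + d × f
- Pooled sensitivity, observed = TP / (TP + FN_B + d × FN_A)
- Pooled NPV, observed = 1 − (FN_B + d × FN_A) / (all PET-negatives)

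At f = 3/225: FN_A = 88 × 3/225 = 1.17; FN_B = 0.59; TP = 132 × 55/225 = 32.27; PET-negatives = 132 × 83/225 = 48.69.

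At f = 5%: FN_A = 4.4; FN_B = 2.2; TP = 132 × (58/225 − 0.05) = 27.43; PET-negatives = 132 × 80/225 + 6.6 = 53.53.

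| Quantity | f = 1.3%: d=0 | d=0.5 | d=1 (true) | f = 5%: d=0 | d=0.5 | d=1 (true) |
|---|---|---|---|---|---|---|
| Unbeneficial rate, arm A | 38.7% | 39.3% | 40.0% | 38.7% | 41.2% | 43.7% |
| Pooled sensitivity | 98.2% | 96.5% | 94.8% | 92.6% | 86.2% | 80.6% |
| Pooled NPV | 98.8% | 97.6% | 96.4% | 95.9% | 91.8% | 87.7% |

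With d = 0, arm A on its own would show 100% sensitivity and 100% NPV.

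**Effect on the primary comparison.** The all-sizes control rate is 167/225 = 74.2%. With d = 0 the apparent difference is 80/225 = 35.6 points. The true difference is 74.2 − 40.0 = 34.2 points at planning values, or 74.2 − 43.7 = 30.6 (from unrounded values) at the 5% ratio.

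**Would growth be seen at month 12?** Section 13.1.2 derives a mean diameter doubling time of 38.5 months (21 to 78) from a series selected for growth. At 38.5 months, one year gives 2^(12/38.5) = 1.24 in diameter and 2^(36/38.5) = 1.91 in volume, above the 50% volume trigger of section 8.3.2. At 78 months it gives 1.11 and 1.38, below both the volume and the 20% diameter triggers.

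**What the control arm can support.** Expected cancers 44 × 58/225 = 11.3; negative scans 44 × 83/225 = 16.2; false negatives 44 × 3/225 = 0.6. The chance of no false negative is (1 − 3/225)^44 = 0.55. With 0 of 16 malignant, the exact 95% upper limit is 1 − 0.025^(1/16) = 21%.

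**The case against.** Several stronger readings are tempting, and the protocol does not support them.

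- *That ultrasound is the only look.* Table 2 also schedules history, clinical examination and, on indication, FNAC at month 12. Section 8.3.5 profiles all cytology and reports a high-risk result in an unoperated patient to the physician. Section 10.1 foresees surgery on clinical suspicion. These routes stand, although the profiling has no stated link to the 12-month window or to endpoint scoring.
- *That everything triggered by the ultrasound is lost.* Section 3 includes FNAC in the 12-month reference standard and makes 12 months a minimum follow-up. No section says that a malignancy found through this work-up is discarded. For later surgery, histology and costs the text is unclear, and that is the part that remains.
- *That pooling is prescribed.* Section 10.3 names no arms. The safety limits use the control arm, and a statistical analysis plan, not seen here, may restrict the accuracy analysis. Pooling is a natural reading of section 10.3, not a stated rule.
- *That the protocol ignores later detection.* Objective SO1c reads the false-negative rate again at five years. Nothing returns that reading to the primary endpoint, accuracy or cost analyses.

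The figures also lean towards the worst case. They cover all sizes, while the primary objective focuses on nodules above 10 mm, where misses should be rarer; Appendix IV reports sensitivity of 100% (92 to 100%) from 15 mm. Section 4.4 does not separate false negatives from false positives above 10 mm, so the calculation cannot be restricted. Sensitivity of 80.6%, implied by the 5% ratio, lies below the pooled interval of 85.6 to 98.9%. Zero detection is the extreme of d.

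Finally, a correction based on the control arm alone is fragile. More often than not it would impute nothing, and one false negative among 16 scans would impute about 2 of 32.

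**Conclusion.** The concern holds in limited form. Verification differs by arm, the main check coincides with the close of the window, and undiagnosed cancers default to benign. The bias favours PET, and the protocol concedes its direction.

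If no arm A missed cancer is confirmed in time, the primary rate is understated by 1.3 points (about 1.2 of 88 patients) at planning values and by 5.0 points (4.4 patients) at the accepted 5% ratio. A reader might infer that the primary result is unsafe. It is not on these figures: the true difference stays above 30 points in both cases.

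The material distortion is in accuracy, if the arms are pooled. A test at the limit of acceptability, with a true NPV of 87.7%, would read 95.9%, close to the planned 96.4%. Costs are biased in the same direction by the protocol's own account, but it gives no basis for a figure. The sizes rest on the assumed d, all nodule sizes, and fixed prevalence and specificity. This is a should-fix, not a must-fix.

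**What to change.** 1. In sections 8.8 and 10.6, state that malignancies and costs arising from the month-12 work-up count in the primary endpoint, accuracy and cost analyses, even when surgery or histology comes after month 12.
2. In section 10.3, take sensitivity, specificity and NPV primarily from the histology-verified control arm, or apply a verification-bias correction such as Begg-Greenes. Label pooled 12-month sensitivity and NPV as upper bounds.
3. Add a sensitivity analysis of the primary endpoint over a range of false-negative fractions among unverified PET-negatives. Include the control-arm estimate with its confidence interval, and update it with the five-year data. It should not replace the primary analysis.

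Patient management is unchanged. The cost is wording and a short extension of data capture from files that section 8.6 already has reviewed; the addendum to section 4.5 reports the trial prolonged to November 2021. The statistical price is wide intervals, since the control arm offers only about 11 cancers and 16 negative scans.

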9. SAFETY REPORTING

9.1 Section 10 WMO event

In accordance to section 10, subsection 1, of the WMO, the investigator will inform the subjects and the reviewing accredited METC if anything occurs, on the basis of which it appears that the disadvantages of participation may be significantly greater than was foreseen in the research proposal. The study will be suspended pending further review by the accredited METC, except insofar as suspension would jeopardise the subjects' health. The investigator will take care that all subjects are kept informed.

9.2 AEs, SAEs and SUSARs

9.2.1 Adverse events (AEs)

Adverse events are defined as any undesirable experience occurring to a subject during the study, whether or not considered related to the experimental intervention (e.g. an AE can also be related to a diagnostic procedure or to an already existing condition). All adverse events reported spontaneously by the subject or observed by the investigator or his staff will be recorded. All AEs are registered on electronic case report forms.

9.2.2 Serious adverse events (SAEs)

A serious adverse event is any untoward medical occurrence or effect that at any dose:

- results in death;
- is life threatening (at the time of the event);
- requires hospitalisation or prolongation of existing inpatients' hospitalisation;
- results in persistent or significant disability or incapacity;
- is a congenital anomaly or birth defect;

Any other important medical event that may not result in death, be life threatening, or require hospitalization, may be considered a serious adverse experience when, based upon appropriate medical judgement, the event may jeopardize the subject or may require an intervention to prevent one of the outcomes listed above.

In case of a SAE, the investigator of the participating centre is responsible for handling and reporting the SAE. All SAEs should be reported to the Study Coordinator within 24h hours of the event. The Study Coordinator will register the SAE and will report the SAEs through the web portal *ToetsingOnline* to the accredited METC that approved the protocol, within 15 days after the sponsor has first knowledge of the serious adverse reactions.

SAEs that result in death or are life threatening should be reported expedited. The expedited reporting will occur not later than 7 days after the responsible investigator has first knowledge of the adverse reaction. This is for a preliminary report with another 8 days for completion of the report.

Exception

A single exception is made to the notification obligation of SAEs: no notification of a SAE is made in case of prolongation of an existing inpatients' hospitalisation due to a postoperative hypocalcaemia, as (mild) hypocalcaemia is a fairly common and expected complication of thyroid surgery. It is usually easily corrected with medication and does not cause persistent damage to the patient. However, in case of severe, possibly life-threatening hypocalcaemia, requiring admission to the ICU or other profound or invasive interventions, a SAE notification will be made as stated above.

